- (3) The weight loss-induced changes in serum ex-vivo bioassay results and serum IGF-1 & IGFBP-1 levels will directly correlate with the proliferative, apoptotic, and IGF axis changes seen in prostate cancer tissue. Specifically, we expect that: (a) Increased weight loss will correlate with a fall in serum IGF-I and a rise in serum IGFBP-1 as well as with a reduction in the ex-vivo proliferation bioassay and increase in ex-vivo apoptosis bioassay. (b) Increased weight loss will correlate with increased apoptosis staining and decreased Ki67 staining in the prostate cancer tissue. (c) The post-intervention change in the serum ex-vivo proliferation and apoptosis bioassays and serum IGF-I and IGFBP-1 levels will directly

correlate with the change in tissue proliferation and apoptosis making these markers clinical tools for secondary prevention prostate cancer weight loss trials.

Objective 1. To evaluate if weight loss prior to radical prostatectomy in overweight and obese men results in antiproliferative and pro-apoptotic effects on prostate cancer tissue histopathology. Overweight and obese men that have elected to undergo radical prostatectomy will be randomized to a control group (no weight loss) vs. a 4-9-week weight loss program followed by radical prostatectomy. Proliferation (Ki67) and apoptosis (TUNEL) of the prostate cancer tissue will be compared between the groups. We will also compare the proliferation and apoptosis indices between the baseline prostate needle biopsy specimens and corresponding radical prostatectomy specimens. In addition, prostate cancer tissue IGF-axis RNA and protein levels (IGF-1, total and phospho-IGF-1 receptor, and down-stream molecules), will be compared between the weight loss and control groups.

Objective 2. To evaluate if weight loss prior to radical prostatectomy in overweight and obese men impacts on the circulating levels of IGF-related analytes and on the Ex-vivo mitogenic and apoptotic activity of patient sera on LNCaP cell lines. The ex-vivo mitogenic and apoptosis bioassay in LNCaP cells will be performed on pre and post sera from the Control Group – No Weight Loss and Weight Loss Group at baseline and prior to radical prostatectomy. In addition we will compare baseline and post-intervention serum IGF-I and IGFBP-1 levels by ELISA.

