Objective 3. To determine if the weight loss-induced changes in the serum biomarkers/bioassays from Objective 2 correlate with prostate tissue histo-marker changes in Objective 1. This analysis will assess if these serum biomarkers can therefore be used as surrogate biomarkers for future large-scale secondary prevention trials in overweight and obese prostate cancer survivors to monitor the success of weight loss intervention. For example, if the degree of LNCaP apoptosis in the ex-vivo apoptosis bioassay correlates with apoptosis in prostate cancer tissue, then the ex-vivo apoptosis bioassay may serve as a useful intermediate bioassay in large-scale trials to monitor the potential efficacy of weight loss in delaying prostate cancer progression or similarly, IGF-I or IGFBP-1 may prove to be the most predictive circulating indicator of prostate tumor apoptosis.

Long-Term Objectives: Our long term objective is to establish weight loss as an effective treatment to slow prostate cancer progression (secondary prevention) in overweight and obese prostate cancer survivors. If our presently proposed trial is found to be positive, indicating that weight loss results in improvements in the proliferative and apoptotic indices in malignant epithelium, our next trial (**intermediate goal**) will be a large scale, multi-site study evaluating if weight loss impacts on PSA doubling time in men with a rising PSA after primary therapy for prostate cancer. Given that PSA doubling time is becoming established as a surrogate for prostate cancer survival, results from this larger scale trial will determine the need for weight loss strategies in overweight and obese prostate cancer survivors.

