Immunostaining and Interpretation: Immunostaining of paraffin embedded pretreatment prostate needle biopsy specimens and malignant tissue from radical prostatectomy specimens will be performed using ki67 monoclonal antibodies (DAKO) and a TUNEL assay (BioVision). The cancer tissue with the highest Gleason grade will be analyzed in a blinded fashion by counting 300 cancer cells per slide. Our main objective (Objective 1 of this proposal) will be to compare the percent of cells staining positive for ki67 and TUNEL between the Control Group-No Weight Loss and Weight Loss Group (controlling for Gleason grade). We will also compare the percent of cells staining for ki67 and TUNEL in the prostate needle biopsy specimen relative to the prostatectomy tissue (also matching for Gleason grade). In addition, we will perform correlation analysis to determine if weight loss correlates with proliferation and apoptosis. We hypothesize that with increasing weight loss there will be decreased ki67 staining and an increasing percentage of cells with TUNEL staining. To further evaluate the effect of weight-loss on prostate tumor staining of the IGF signaling cascade we will analyze immunostaining of phospho-IGF-1R (using a Cell Signaling antibody) and phospho-Akt (Cell Signaling). We will also evaluate for earlier stages of apoptosis as measured by activated caspase-3 (Oncogene). If we detect changes in apoptosis, we will also stain for BAX and BCL2 using antibodies from R&D. If we detect changes in proliferation as measured by ki67 staining, we will also stain for Mcm-2 (which has been shown to be a prognostically important prostate cancer proliferation marker) using antibodies from R&D.⁶⁶

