Secondary Statistical Analyses: The statistical methods for these analyses will be analysis of variance (ANOVA), linear regression, and correlation analysis. ANOVA will be used to determine if the serum biomarkers (IGF-I, IGFBP-1, proliferation and apoptosis bioassays) change over the course of time. These models will include a term for time, treatment (weight-loss versus no weight loss) and the time by treatment interaction effect. We will also construct ANOVA models for weight and body fat over time to determine if the treatment by time effect (intervention effect) is significant. Next, linear regression models will be constructed for each biomarker to assess the factors that predict change in that marker. Predictors will include actual weight loss (percent change), group, grade, PSA, percent body fat, and demographic factors. These models will allow us to assess the direct effect of weight loss on each of the serum biomarkers and allow for the assessment of whether weight change or intervention is the primary factor predicting change in the biomarkers. This assessment is required due to the fact that the intervention will have varying effects on weight based on the amount of subject compliance with the weight loss regime. Regression models will also be constructed to compare the groups with respect to the pre-prostatectomy biomarkers and the tissue markers and the between group tissue markers (apoptosis, Ki67 staining). A separate model will be constructed for each marker including the predictors of group, grade, PSA, percent body fat and demographic factors. Next, we will construct regression models to determine if the biomarkers, or change in biomarkers, affect the post-op pathology. Ordinal regression will be used for post-op pathology. These models will include terms for the demographic factors and for each of the biomarkers. Since there are a large number of biomarkers we will first construct single biomarker models which will include the covariates for each outcome and then combine together all significant markers into multiple regression models. Finally, we will use the Spearman correlation to test for correlations between pre-prostatectomy biomarkers and the tissue markers. This analysis will specifically address **Objective 3** of the proposal, that being to determine if a correlation exists between serum biomarkers and tissue biomarkers. The Spearman correlation is a non-parametric rank based correlation measure that does not depend on the assumption that the markers are normally distributed.

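### Objective 3 asks whether serum changes track tissue changes, but no planned analysis relates serum change to Ki67 or TUNEL

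*Combined protocol and SAP*

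**What the plan says.** The Rationale states Objective 3 as "To determine if the weight loss-induced changes in the serum biomarkers/bioassays from Objective 2 correlate with prostate tissue histo-marker changes in Objective 1". Hypothesis 3(c) expects the post-intervention change in the two bioassays, IGF-I and IGFBP-1 to "correlate with the change in tissue proliferation and apoptosis making these markers clinical tools for secondary prevention prostate cancer weight loss trials". Both sides of the relation are changes.

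Under Secondary Statistical Analyses, the analysis assigned to Objective 3 is "we will use the Spearman correlation to test for correlations between pre-prostatectomy biomarkers and the tissue markers". The same paragraph restates the objective as "that being to determine if a correlation exists between serum biomarkers and tissue biomarkers", with no mention of change on either side.

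The data for a change analysis are already planned. Serum Studies has the IGF analytes and bioassays measured at baseline and before surgery in both arms. Immunostaining and Interpretation has Ki67 and TUNEL on biopsy and prostatectomy tissue, matched for Gleason grade. Secondary Outcome Variables lists the serum IGF change and the biopsy-to-prostatectomy change in both tissue indices.

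**The concern.** Objective 3 is the stated basis for choosing serum markers to monitor weight loss in later large trials. For that use, a marker's movement under the intervention has to say something about the tissue's movement. A correlation of values at one time can arise because some men have, for example, both high IGF-1 and high proliferation for reasons that existed before randomization. A marker could then be taken forward although its change carries no information about tissue, or dropped although it does. If the change analysis is added only after the data are seen, the choices of tissue area, unmatched pairs and arm adjustment will be post hoc.

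**Working it through.** **Step 1. Does any other planned analysis fill the gap?**

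| Planned analysis | Role of serum change | Role of Ki67/TUNEL |
|---|---|---|
| Time-by-treatment ANOVA | Outcome | None |
| "linear regression models will be constructed for each biomarker to assess the factors that predict change in that marker" (weight loss, group, grade, PSA, body fat, demographics) | Outcome | None |
| Tissue-marker regressions: "A separate model will be constructed for each marker including the predictors of group, grade, PSA, percent body fat and demographic factors" | None; no IGF marker or bioassay | Outcome |
| Models of "if the biomarkers, or change in biomarkers, affect the post-op pathology" | Predictor | None; the outcome is ordinal |
| Immunostaining: "we will perform correlation analysis to determine if weight loss correlates with proliferation and apoptosis" | None; weight loss is used | Outcome |
| Spearman analysis for Objective 3 | None stated | Correlated with pre-surgery serum |

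No row has serum change and Ki67 or TUNEL together.

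**Step 2. The plan's own power figure (context only).** With 30 v 30 and effect size 0.74, the noncentrality is 0.74 × √(30/2) = 2.87 on 58 df, which gives 80.5% power. The stated 80% reproduces. No power is given for Objective 3.

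**Step 3. How level and change correlations differ.** The inputs below are assumptions; the documents give none of them. Baseline = trait + error and post = trait + change + error, with true variance at the second time set to 1. Let h be the trait share, e_s and e_t the serum and tissue error variances, and r_T and r_C the trait and change correlations. Then:

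- level r = [h·r_T + (1−h)·r_C] / √[(1+e_s)(1+e_t)]
- change r = (1−h)·r_C / √[(1−h+2e_s)(1−h+2e_t)]

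Changes unrelated (r_C = 0, r_T = 0.4), no arm effect, n = 60, simulated two-sided 0.05 Spearman test:

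| h | e_s, e_t | level r | level significant | change significant |
|---|---|---|---|---|
| 0.5 | 0, 0 | 0.20 | 31% | 5% |
| 0.7 | 0, 0 | 0.28 | 54% | 5% |
| 0.5 | 0.3, 0.5 | 0.20/√1.95 = 0.14 | 17–18% | 5% |
| 0.7 | 0.1, 0.3 | 0.28/√1.43 = 0.23 | 40% | 5% |

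Changes related (r_C = 0.5, r_T = 0), with error, h 0.5–0.7: level 12–33%; change 17–55% at n = 60 and 14–44% if only 45 pairs are evaluable. For example, with h = 0.5 and errors 0.1 and 0.3, level r = 0.25/√1.43 = 0.21 and change r = 0.25/√(0.7×1.1) = 0.28.

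**Step 4. Treatment arm.** If both markers shift with arm, they correlate across the pooled sample even with no link within arms. With 30 per arm, shifts d_s and d_t add 0.25·d_s·d_t to the covariance and 0.25·d² to each variance. Take d_t = 0.74 (the effect size in Sample Size Determination), h = 0.5, e_s = 0.1, e_t = 0.3, r_T = 0.4 and r_C = 0:

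| d_s | unadjusted change r | change significant | level r | level significant |
|---|---|---|---|---|
| 0.5 | 0.0925/√(0.7625×1.2369) = 0.10 | 11% | 0.2925/√(1.1625×1.4369) = 0.23 | 39% |
| 1.0 | 0.185/√(0.95×1.2369) = 0.17 | 27% | 0.385/√(1.35×1.4369) = 0.28 | 55% |
| 1.5 | 0.2775/√(1.2625×1.2369) = 0.22 | 43% | 0.4775/√(1.6625×1.4369) = 0.31 | 66% |

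Adjusting change-on-change for arm brings it back to about 5%.

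**Step 5. Precision.** Detectable r at 80% power = tanh[(1.960+0.842)·√(1.06/(n−3))] = 0.36 with 60 pairs, 0.42 with 45 and 0.50 with 30. With 300 cells counted and an assumed index of 1–5%, counting error √[p(1−p)/300] is 0.6–1.3 percentage points per specimen, and √2 times that, 0.8–1.8, for a difference.

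**The case against.** The strongest reply is that the plan uses *change* loosely. Objective 1's main contrast is prostatectomy tissue between randomized arms, and the biopsy comparison is an addition to it. Both illustrations in the Objective 3 text, the LNCaP apoptosis bioassay and IGF-I or IGFBP-1 as an indicator of tumor apoptosis, are worded as levels. This stands in part: how tissue should be expressed is arguable, and the planned correlation does serve those examples. It does not rescue the serum side, where pre and post sera are explicit and change is never set against Ki67 or TUNEL.

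One could also read pre-prostatectomy biomarkers as including change, or post-operative pathology as including the indices. The wording is against both. The same paragraph names change separately where it means change. It assigns post-operative pathology to ordinal regression, while the staining indices are percentages of cells with models of their own.

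Change scores are noisy. With tissue error variance 1.0 and serum 0.3, related changes give level 10–21% and change 11–20% at n = 60. Where traits and changes both correlate, the level test rejects more often (63–81% v 17–56%). That is correct, and it limits what the fix can promise.

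Finally, adjusting for arm removes the part of the association that the intervention itself creates, which some would count as evidence for a surrogate. But any two markers that respond to the arm would show it, so both versions should be reported.

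**Conclusion.** The concern holds as a mismatch between a named secondary objective and its analysis. No planned analysis relates serum change to Ki67 or TUNEL. This rests on the text alone and needs no simulation. The fix should be made before analysis.

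A reader might infer three stronger things, and the documents support none of them:

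- *Objective 3 is left without any relevant analysis.* The level correlation matches the illustrations given for the objective and covers part of it.
- *A change-on-change test would be more powerful and would always hold its 5% error rate.* Its power ranges from above to below that of the level test under plausible inputs. The 5% holds only without an arm effect or after adjustment for arm; unadjusted, it was 11%, 27% and 43% in the cases shown.
- *The trial's main result is affected.* The primary comparison of apoptotic index does not use this analysis.

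The percentages are illustrations on assumed trait shares, correlations, error variances and serum shifts. Only the 0.74 tissue effect and the 60 evaluable men come from the plan.

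**What to change.** In Secondary Statistical Analyses, for Objective 3:

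1. Add the Spearman correlation of serum change (pre-surgery minus baseline; IGF-1, IGFBP-1 and the two bioassays) with tissue change (prostatectomy minus biopsy; TUNEL and Ki67). Use the Gleason-grade matching already planned. State which prostatectomy area is used when the biopsy grade is not the highest grade, and how unmatched pairs are handled.
2. Make the arm-adjusted partial rank correlation the main result, with the unadjusted one beside it.
3. Add, with the same adjustment, serum change against prostatectomy TUNEL and Ki67. This needs no biopsy pair and keeps all evaluable men.
4. Keep the planned level correlation as supportive.
5. Report 95% confidence intervals and the number of evaluable pairs. Label the 4 × 2 = 8 correlations exploratory or state a multiplicity rule; if independent, the chance of at least one false positive is 1 − 0.95⁸ = 34%.
6. Align the restatement of Objective 3 with the Rationale, and state that a non-significant result does not rule out a marker.

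The cost is wording only, with no new samples or visits. The price is that men without a grade-matched biopsy pair drop out of item 1, and that its estimates will be imprecise.

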Statistical Design: The statistical design of this study is a randomized repeated measures utilizing random mixed block sizes known only to the statistician constructing the randomization list to assign subjects to two study arms in a ratio of 7:6, weight loss to no weight loss.

Sample Size Determination: An evaluable sample of at least 60 subjects (no weight loss=30, weight loss=30) is expected to provide 80% power to detect an effect size of 0.74 using a two group t-test with a 0.050 two-sided significance when comparing the apoptotic index (primary outcome variable) in the radical prostatectomy malignant epithelium between the weight loss and no Weight Loss Group. The apoptotic index will be measured in the malignant epithelium with the highest Gleason grade. To account for a post-randomization attrition rate of up to 15% in the Weight Loss Group, a total of 35 subjects will be randomized to the Weight Loss Group, thus bringing the total sample size to 65 subjects. Kim et al. observed an effect size of 1.74 on apoptotic index using a nutritional intervention in a similar study.⁶⁴

Data Analysis: Data analyses will be performed on randomized subjects who complete the study. All parameters measured will be summarized descriptively. The number of subjects, mean, standard error of the mean, median and min-max values will be presented for continuous parameters and the number and percentage of subjects in each category will be presented for categorical parameters. No imputation of missing data is planned. Demographic and baseline characteristics will be summarized using descriptive statistics overall and by treatment group to assess baseline comparability. Treatment groups will be compared using the appropriate nonparametric tests for categorical parameters and analysis of variance models for continuous parameters.

Primary Outcome Variable: The primary outcome variable is apoptotic index of the highest Gleason grade malignant epithelium in the radical prostatectomy specimen. The primary objective is to compare the mean apoptotic index between the Weight Loss Group and the Control Group-No Weight Loss. The two independent sample t-test will be used to compare the index between the groups. If the index is non-normally distributed we will use the Wilcoxon rank sum test. Next, linear regression models will be constructed to test whether the treatment effect

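### The Objective 3 Spearman test specifies no adjustment for arm, so a serum marker and a tissue marker can correlate only because the programme moves both

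*Combined protocol and SAP*

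**What the plan says.** Section 3, Secondary Statistical Analyses, ends with the test assigned to Objective 3: "we will use the Spearman correlation to test for correlations between pre-prostatectomy biomarkers and the tissue markers". Arm is not mentioned: there is no adjustment, no stratification and no separate coefficient by group.

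Section 1, Objective 3, states the use to be made of the result: "This analysis will assess if these serum biomarkers can therefore be used as surrogate biomarkers".

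Section 3, Immunostaining and Interpretation, adds a second correlation, also without reference to arm: "we will perform correlation analysis to determine if weight loss correlates with proliferation and apoptosis".

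The other models in Secondary Statistical Analyses are these:

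- Regressions for change in each biomarker, with percent weight change and group both as predictors. The explanatory text ties these to the serum biomarkers.
- One model per marker comparing the groups, with group, grade, PSA, percent body fat and demographics as predictors. Neither IGF analyte and neither bioassay is listed as a predictor of a tissue marker.
- Ordinal regressions with the biomarkers as predictors. The outcome is post-operative pathology, and no group term is listed.

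**The concern.** The trial's hypotheses are that the programme lowers proliferation and raises apoptosis in the tumour, and that it also moves serum IGF-I, IGFBP-1 and the bioassays. When two groups differ in the mean of two variables, those variables are associated in the combined sample even if they are unrelated within each group. An unadjusted correlation mixes that between-arm component with the association among men treated alike.

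The plan would use the result to nominate serum markers for later trials. A marker that says nothing about an individual's tumour could then be nominated more often than the nominal error rate allows. This happens in the very situation that the trial hopes to demonstrate.

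The correlation of weight loss with Ki67 and TUNEL is exposed in the same way. Arm is expected to drive much of the variation in weight loss, so that correlation partly repeats the arm comparison and is not clean evidence of dose-response.

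**Working it through.** **The plan's own figure.** Sample Size Determination says that 30 evaluable men per arm "is expected to provide 80% power to detect an effect size of 0.74", "using a two group t-test with a 0.050 two-sided significance". The exact noncentral t calculation (58 df, noncentrality 0.74 × √15 = 2.866) gives 80.5%, so the figure reproduces. Applying the "post-randomization attrition rate of up to 15% in the Weight Loss Group" to the 35 men randomised there gives 35 × 0.85 = 29.75, so 30 per arm is a fair basis for what follows.

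**Inputs.**
- From the documents: 30 per arm, and a tissue shift d_t = 0.74 SD.
- Assumed: a two-sided 0.05 level for the Spearman test (none is stated); serum shifts d_s of 0.3 to 1.74 SD (the documents give direction only); normal markers, independent within arm.

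**Induced correlation.** With equal arms, the arm difference adds d²/4 to each variance and d_s·d_t/4 to the covariance. Hence

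r = 0.25·d_s·d_t / √[(1 + 0.25·d_s²)(1 + 0.25·d_t²)].

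For d_s = d_t = 0.74: 0.1369 / 1.1369 = 0.12. For d_s = 1.74: 0.3219 / √(1.7569 × 1.1369) = 0.3219 / 1.413 = 0.23.

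**Rejection rates by simulation, no within-arm link, d_t = 0.74.**

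| Assumed serum shift (SD) | Induced r | Unadjusted Spearman significant | Arm partialled out |
|---|---|---|---|
| 0 | 0.00 | about 5% | about 5% |
| 0.3 | 0.05 | about 7% | about 5% |
| 0.5 | 0.08 | about 10% | about 5% |
| 0.74 | 0.12 | about 15% | about 5% |
| 1.2 | 0.18 | about 28% | about 5% |
| 1.74 | 0.23 | about 45% | about 5% |

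If the serum marker moves and the tissue does not, the unadjusted rate is again about 5%. The test is two-sided, so the direction of the shifts does not matter.

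**Weight loss against tissue.** Take an arm difference of 5 points. This is the midpoint of the 4-6% loss anticipated in section 3, with no loss in controls, in line with the plan's expectation. Assume a within-arm SD of 2 to 3 points. The standardised shift is then 5/3 = 1.67 to 5/2 = 2.5. The share of weight-loss variance explained by arm is 0.25d²/(1 + 0.25d²): 0.694/1.694 = 41% to 1.5625/2.5625 = 61%. With no dose-response and d_t = 0.74, the unadjusted test is significant in about 43% to 59% of trials.

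**Power given up by adjusting.** When the arms do not differ, partialling out arm lowers power from about 60% to 59-60% for a true correlation of 0.3, and from about 86% to 85% for 0.4. A smaller simulation put the first loss at 3 points (62% to 59%).

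**The case against.** Five points can fairly be made for the plan.

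- **Pooling is not stated.** A reader might infer that the plan prescribes a pooled analysis. It does not; it is silent on arm. Pooling is the natural reading of an unqualified correlation, but what can be said is that no adjustment is specified.
- **The markers need not correlate.** A reader might also infer that a spurious correlation is bound to appear. With equal shifts of 0.74 SD the unadjusted test is non-significant in about 85% of trials, and the induced coefficient over the shifts considered is only 0.05 to 0.23. Both markers must move for there to be any inflation.
- **The plan recognises the issue in part.** It includes regressions with weight loss and group together, to separate weight change from assignment. That stands for the serum biomarkers. Extending it to Ki67 and TUNEL would be a reading that the text does not clearly support.
- **The between-arm component has some meaning.** Objective 3 concerns changes induced by weight loss and markers to monitor an intervention. A marker that the programme moves strongly is not worthless for monitoring, and a within-arm association does not by itself establish surrogacy. This is a good reason to show both coefficients, but not to rely on the unadjusted one alone.
- **The aim is secondary.** Objective 1 and the sample size are untouched, and some of the language about surrogates is tentative.

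Requiring significance in each arm would be a poor remedy. For a true within-arm correlation of 0.3, one arm of 30 is significant in about 33% of trials, so both are significant in about 0.33² = 11%.

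**Conclusion.** The point holds in this form: the only test assigned to Objective 3 specifies no adjustment for arm, and no other planned model supplies the serum-tissue association given group. If the programme shifts both markers, an uninformative serum marker passes the unadjusted test in about 7% to 45% of trials at the design tissue effect, against about 5% after adjustment. If only one marker moves, there is no inflation.

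The size depends on assumed serum shifts of 0.3 to 1.74 SD, an assumed 0.05 two-sided level and normal markers. The 43% to 59% for weight loss against tissue depends on an assumed SD of 2 to 3 points. The documents do not support saying that the plan mandates pooling or that a false correlation is certain. The matter should be corrected because the result is meant to guide the choice of markers for later trials, but it does not affect the primary analysis.

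**What to change.** In Secondary Statistical Analyses, define the Objective 3 test as a Spearman correlation with arm partialled out, or as a regression of the tissue marker on the serum marker plus group. Report each arm's coefficient with a 95% CI, and show the unadjusted coefficient alongside, labelled descriptive.

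Treat the weight-loss correlations in Immunostaining and Interpretation in the same way, or extend the planned regression on weight loss plus group to Ki67 and TUNEL.

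State that any claim about a candidate surrogate rests on the single combined arm-adjusted estimate. It should not require significance in each arm, and it should not rest on the unadjusted coefficient alone.

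The same edit could settle a related mismatch: Objective 3 speaks of changes in the markers, while the named test uses pre-prostatectomy serum values.

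The cost is SAP wording and about 1 point of power (at most about 3). No data, visits or patients are added.
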